1.0 BACKGROUND AND RATIONALE

1.1 Study Synopsis

Currently, there is no standard of care for those diagnosed with intermediate risk head and neck squamous cell carcinoma (HNSCC), defined as locally advanced disease with risk features other than extracapsular extension (ECE) or positive margins. Most commonly they are treated with either radiotherapy alone or with concurrent chemo-radiotherapy (cCRT) in the post-surgical setting, with no high level evidence to define which should have chemotherapy added to adjuvant radiotherapy. In patients receiving cCRT, cisplatin is most commonly used. The clinical benefit of cisplatin with radiation therapy in this patient population is questionable and the rate of serious toxicity is high. To address the unmet need for improving systemic treatment options, this multi-center, single arm Phase II trial will evaluate the feasibility of combining radiation therapy with durvalumab as adjuvant therapy for patients with intermediate risk HNSCC.

A total of 18 evaluable subjects will be accrued as depicted in the study schema. The treatment regimen will administer Q3 weekly flat dosing durvalumab (1500 mg) with radiation therapy in cycles 1-3, followed by single agent durvalumab (1500 mg) Q4 weekly for an additional three cycles. Our hypothesis is that durvalumab combined with radiation will have improved 3-year disease free survival (DFS) compared to historical control. Secondarily, we predict there will be fewer Grade 3-5 acute toxicities compared to the combination of radiation therapy and cisplatin. Tissue and blood based correlative studies will characterize the tumor microenvironment both at pre-treatment and in the event of recurrence.

Study Schema

*Radiation therapy is administered per standard radiation oncology regimens, on a daily basis and/or as scheduling during a Monday-Friday work week. Radiation therapy is given concurrently with durvalumab during Cycles 1-3. Durvalumab treatment Cycles 1-3 are 3-week long cycles (total of 9 weeks). Radiation therapy will be delivered at a dose of 2 Gy over 30 fractions totaling a final dose of 60 Gy. Radiation treatment will take 6 weeks (Monday-Friday) or 30 days and occurs for 6 of 9 weeks that define Cycles 1-3. However, due to delays or missed appointments, completion of those

30 fractions may take longer than the allotted 6 weeks and this is allowed. Radiation therapy must be scheduled and completed within Cycels 1-3 and should not extend into Cycle 4.

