3.0 Criteria for Evaluation / Study Endpoints

3.1 Primary Endpoint

- 3.1.1 3-year DFS will be estimated via the Kaplan-Meier method. DFS is defined as the time from D1 of treatment to time of disease recurrence or death.

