9.2 Sample Size, Accrual and Duration of Accrual

Our evaluable study sample size (N_{total}) is 17, and we will enroll 18 to allow for possible non-evaluable patients. Based on a historical control of 10yr DFS is 19% (Cooper, RTOG 1016), the 3 year DFS is approximated to be 60.8%. Based on this calculation, we will need a sample size of 17 patients, to detect a 23% difference in 3 year DFS with 80% power (table below) and one-sided alpha of 0.1.

Difference from Historical Control	10%	20%	23%	25%
Test significance level, α	0.050	0.050	0.010	0.050
1 or 2 sided test?	1	1	1	1
Null hypothesis proportion, π_0	0.608	0.608	0.608	0.608
Alternative proportion, π_A	0.708	0.808	0.838	0.858
Power (%)	80	80	80	80
n	141	33	17	20

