9.3 Data Analysis Plans

Analytic plan for secondary objective:

The rate of grade 3-5 acute toxicity will be tabulated as described above to determine whether the criterion for safety has been met. A confidence interval for this rate will be calculated based on the methods of Koyoma T, and Chen H. Rates of individual types/grades of toxicities will also be reported [30].

Median DFS will be estimated using the Kaplan Meier method.

Analytic plan for additional secondary objective:

1. Grade 3-5 chronic toxicities will be tabulated by type and grade.
2. Median OS will be estimated using the Kaplan Meier method.
3. PD-L1 expression will be measured from baseline tumor sample using IHC. Expression will be correlated with DFS using the Kaplan Meier method. A

Log-rank test will compare DFS between those with and without PD-L1 expression.

Analytic plan for exploratory Objectives:

1. HPV status will be measured per institutional SOC, typically p16 and/or HPV FISH. The Kaplan Meier method will be used and a Log-rank test will compare DFS between HPV positive/negative patients.
2. Tumor infiltrating level (TIL) expression will be measured by flow cytometry at baseline and if possible at tumor recurrence. These levels will be compared at these time points using paired t-tests (pre vs final post assessment) or longitudinal models that account for repeated assessments when available. These models can be broadened to allow for comparisons to be made across the 4-response groups (CR/PR/SD/PD) using analysis of covariance models with baseline assessments being the covariate in the model.

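### Section 9.2 gives the chosen design a one-sided alpha of 0.1 in the text and 0.010 in the table; only 0.10 yields n=17, and no cut-off on a 36-month count out of 17 meets both 10% and 80%

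*Combined protocol and SAP*

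**What the plan says.** Section 9.2 compares 3-year DFS with a historical value of 60.8%. For the chosen design the text says the sample is sized "to detect a 23% difference in 3 year DFS with 80% power (table below) and one-sided alpha of 0.1". The table below it has four columns, for differences of 10%, 20%, 23% and 25%, all one-sided at 80% power. Its alpha row reads "Test significance level, α 0.050 0.050 0.010 0.050", so the 23% column, which is the chosen design, carries 0.010. That column gives a null of 0.608, an alternative of 0.838 and n=17.

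On the analysis, Section 3.1 says "3-year DFS will be estimated via the Kaplan-Meier method". Section 9.3 says "Median DFS will be estimated using the Kaplan Meier method", under a heading for the secondary objective. Neither section names a test of 3-year DFS against 60.8% or a cut-off for success.

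On the count, Section 9.2 says the evaluable sample "is 17, and we will enroll 18 to allow for possible non-evaluable patients". Section 1.1 says "A total of 18 evaluable subjects will be accrued as depicted in the study schema".

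**The concern.** Section 9.2 is the only place where the trial's error rates are stated, and its text and table differ tenfold on alpha for the design actually chosen. A reader who relies on the table would believe the trial works to a 1% false-positive standard when it was sized at 10%. The table is also implausible on its face: at the same power, a smaller difference (23% against 25%) with a stricter alpha (0.010 against 0.050) cannot need fewer patients (17 against 20).

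Section 1.1 states a hypothesis of improved 3-year DFS over historical control, so the result will be judged against 60.8%. Without a named test, the stated 10% and 80% belong to no rule. With 17 patients a count moves in coarse steps, so one patient can decide success or failure.

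**Working it through.** **Inputs (Section 9.2).** Null p0 = 0.608; alternative p1 = 0.708, 0.808, 0.838 or 0.858; one-sided test; power 80% (z = 0.8416).

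**Step 1: reproduce the table.** The one-sample normal-approximation formula is

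n = [(z_alpha·√(p0(1−p0)) + z_power·√(p1(1−p1))) / (p1−p0)]², rounded up.

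| Difference | Alpha used | n computed | n printed |
|---|---|---|---|
| 10% | 0.05 | 140.58 → 141 | 141 |
| 20% | 0.05 | 32.18 → 33 | 33 |
| 25% | 0.05 | 19.25 → 20 | 20 |
| 23% | 0.10 | 16.55 → 17 | 17 |
| 23% | 0.05 | 23.42 → 24 | 17 |
| 23% | 0.010 | 39.52 → 40 | 17 |

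For the 23% column, √(0.608×0.392) = 0.4882 and √(0.838×0.162) = 0.3684.

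- Alpha 0.10: (1.2816×0.4882 + 0.8416×0.3684)/0.23 = 4.07, and its square is 16.55.
- Alpha 0.010: (2.3263×0.4882 + 0.8416×0.3684)/0.23 = 6.29, and its square is 39.5.

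Other versions of the formula (two-sided, null-only or alternative-only variance, arcsine, continuity-corrected) give between 26 and 47 at alpha 0.010, never 17.

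**Step 2: nominal power at n=17.** Power = Φ[((p1−p0)√n − z_alpha·√(p0(1−p0))) / √(p1(1−p1))]. This is 80.9% at alpha 0.10 and 30.6% at alpha 0.010.

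**Step 3: exact error rates for a 36-month count.** Assume 36-month status is known for every patient and success means at least r disease free. Alpha is P(X ≥ r) under Binomial(n, 0.608), and power is the same tail under Binomial(n, 0.838).

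| Rule | Exact alpha | Exact power |
|---|---|---|
| ≥13/17 | 14.0% | 87.3% |
| ≥14/17 | 5.3% | 70.8% |
| ≥14/18 | 10.6% | 84.6% |
| ≥15/18 | 3.8% | 66.8% |
| ≥15/19 | 7.9% | 81.7% |

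No cut-off at 17 or 18 gives alpha ≤10% together with power ≥80%. The smallest n that does is 19.

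**Step 4: the z-test implied by the sizing formula.** z = (r/17 − 0.608)/√(0.608×0.392/17). At 12/17, z = 0.83 (p = 0.204). At 13/17, z = 1.32 (p = 0.093). This test therefore rejects at 13/17 at nominal 0.10, where the exact alpha is 14.0%.

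**Step 5: a test of the whole curve.** Take a one-sample log-rank statistic (O−E)/√E with n=17, exponential DFS (hazards −ln(0.608)/3 and −ln(0.838)/3 per year), no dropout, and a nominal 0.10 cut-off. By simulation (400,000 runs):

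- 5 years of follow-up per patient: alpha 8.4%, power 90.7%.
- 3 years of follow-up per patient: alpha 8.1%, power 77.3%. With the cut-off recalibrated to alpha 10.0%, power is 81.0%.

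**The case against.** The strongest reply is that the alpha entry is a one-cell misprint that changes nothing. The text, the two proportions, the power and n=17 all agree at 0.10, and nobody intended a design at 0.010. That is right as far as n goes. The printed error rate is still wrong, in the only section that states it.

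On the exact figures, the reply is that the normal approximation is a standard sizing method and that small-sample discreteness affects every column. With the largest rejection region keeping exact alpha within 0.05, exact power is 79.0% at n=141, 70.8% at n=33 and 68.6% at n=20. This also stands: n=17 is not a miscalculation.

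The count out of 17 is, moreover, not a rule the protocol states. The primary objective is framed as estimation, and a Kaplan-Meier estimate with censoring is not a simple fraction. Section 7.6 calls DFS dichotomous, but that describes how recurrence is assessed. The Section 9.3 sentence concerns median DFS and says little about a 3-year test. The 60.8% matches 0.19^(3/10) = 0.6076, which suggests exponential DFS was already assumed, and Section 5.9 allows up to 5 years of follow-up. Under those conditions a one-sample log-rank test meets both stated figures.

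So the exact binomial results are conditional on a count. The reply does not supply the missing test; it shows how much the error rates at n=17 depend on which test is chosen.

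**Conclusion.** The concern holds.

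- **Alpha.** The 0.010 in the 23% column is wrong and should read 0.100. This rests on the one formula that reproduces the whole table. The sample size is unaffected.
- **Error rates.** The 10% and 80% are nominal. For a 36-month count with all 17 statuses known, the choice lies between an alpha 4 points above the stated value (14.0%, at ≥13/17) and a power about 9 points below it (70.8%, at ≥14/17). This does not extend to whole-curve tests, which can meet both figures under exponential DFS with enough follow-up. The defect is that no test is named, so the stated rates cannot be tied to a rule.
- **Count.** The 18 evaluable patients in Section 1.1 conflict with the 17 evaluable and 18 enrolled in Section 9.2. This is minor alone, but the available cut-offs and their alphas differ between 17 and 18.

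**What to change.** 1. In the Section 9.2 table, change 0.010 to 0.100 in the 23% column.
2. Before analysis, name the primary test and its cut-off in Section 9.2, and replace the nominal 10% and 80% with that rule's own figures. Options without added patients:
   - At least 14/17 disease free at 36 months: alpha 0.053, power 71%. This keeps alpha within 0.10.
   - If all 18 are evaluable, at least 14/18: alpha 0.106, power 84.6%. The stated alpha must then be revised.
   - A whole-curve test such as the one-sample log-rank: say so, and state the exponential assumption, the follow-up per patient and the resulting alpha and power.
3. Make Section 1.1 and Section 9.2 agree on the evaluable and enrolled numbers.

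The cost is one table cell, a sentence or so in Section 9.2 and one word in Section 1.1. No patients are added. If a 36-month count with alpha within 0.10 is chosen, the stated power drops from 80% to 71%.

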9.3 Data Analysis Plans

Analytic plan for secondary objective:

The rate of grade 3-5 acute toxicity will be tabulated as described above to determine whether the criterion for safety has been met. A confidence interval for this rate will be calculated based on the methods of Koyoma T, and Chen H. Rates of individual types/grades of toxicities will also be reported [30].

Median DFS will be estimated using the Kaplan Meier method.

Analytic plan for additional secondary objective:

1. Grade 3-5 chronic toxicities will be tabulated by type and grade.
2. Median OS will be estimated using the Kaplan Meier method.
3. PD-L1 expression will be measured from baseline tumor sample using IHC. Expression will be correlated with DFS using the Kaplan Meier method. A

Log-rank test will compare DFS between those with and without PD-L1 expression.

Analytic plan for exploratory Objectives:

1. HPV status will be measured per institutional SOC, typically p16 and/or HPV FISH. The Kaplan Meier method will be used and a Log-rank test will compare DFS between HPV positive/negative patients.
2. Tumor infiltrating level (TIL) expression will be measured by flow cytometry at baseline and if possible at tumor recurrence. These levels will be compared at these time points using paired t-tests (pre vs final post assessment) or longitudinal models that account for repeated assessments when available. These models can be broadened to allow for comparisons to be made across the 4-response groups (CR/PR/SD/PD) using analysis of covariance models with baseline assessments being the covariate in the model.

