2.0 STUDY OBJECTIVES

2.1 Primary Objective

2.1.1 To estimate median 3-year disease free survival (DFS) in patients with intermediate-risk HNSCC treated with adjuvant durvalumab with radiotherapy.

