9.0 STATISTICAL CONSIDERATIONS

9.1 Study Design/Study Endpoints

Primary endpoint is to estimate median 3 year disease free survival (DFS) in patients with intermediate-risk HNSCC treated with adjuvant durvalumab with radiotherapy.

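### Section 9.3 analyses median DFS, while the trial is defined and sized on 3-year DFS; the test or interval for 3-year DFS against 60.8% is not named

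*Combined protocol and SAP*

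**What the plan says.** - **Hypothesis (1.1):** "Our hypothesis is that durvalumab combined with radiation will have improved 3-year disease free survival (DFS) compared to historical control".
- **Primary objective (2.1.1):** "To estimate median 3-year disease free survival (DFS) in patients with intermediate-risk HNSCC treated with adjuvant durvalumab with radiotherapy". Section 9.1 words the primary endpoint in the same way.
- **Primary endpoint (3.1.1):** "3-year DFS will be estimated via the Kaplan-Meier method", with time counted from day 1 of treatment to recurrence or death.
- **Sizing (9.2):** 17 evaluable patients, "to detect a 23% difference in 3 year DFS with 80% power", against a null of 60.8% at one-sided alpha 0.1. The 23% column of the table prints alpha as 0.010.
- **Number of patients:** 9.2 has 17 evaluable and adds that "we will enroll 18 to allow for possible non-evaluable patients". Section 1.1 says "A total of 18 evaluable subjects will be accrued as depicted in the study schema".
- **Analysis (9.3):** there are headings for secondary, additional secondary and exploratory objectives, and none for the primary. The only DFS statement for the whole cohort is "Median DFS will be estimated using the Kaplan Meier method". The other DFS lines are log-rank comparisons by PD-L1 and HPV status.
- **Follow-up (5.9):** up to 5 years after removal from study treatment.

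**The concern.** A median is a time and 3-year DFS is a probability, so the wording in 2.1.1 and 9.1 does not define one quantity. Section 9.3 then takes up the median, which cannot be compared with 60.8%. If the regimen works as hoped, that median will probably not be reached during follow-up. The analysis the sample size was built for, 3-year DFS against 60.8%, has an estimator in 3.1.1. It has no named test, no interval method and no stated handling of patients censored before 3 years. With 17 or 18 patients, the choice of method can decide whether a plausible result counts as better than the historical control.

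**Working it through.** **Inputs.** From 9.2: p0 = 0.608, p1 = 0.608 + 0.23 = 0.838, one-sided alpha 0.10 (text) or 0.010 (table), power 80%, n = 17 (18 enrolled). From 5.2.1: treatment lasts 3×3 + 3×4 = 21 weeks. From 5.9: up to 5 years of follow-up after treatment.

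**1. Reproducing the plan's n.** One-sample proportion, normal approximation:

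n = [(z_alpha·√(p0(1−p0)) + 0.8416·√(p1(1−p1))) / (p1−p0)]²

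- alpha 0.10: [(0.6256 + 0.3101)/0.23]² = 16.55, so 17. This matches.
- alpha 0.010: 39.5, so 40.
- The same formula at alpha 0.05 gives the table's 141, 33 and 20 for the other columns.

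So 17 belongs to alpha 0.10, and the printed 0.010 is an error.

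**2. Cut-off implied by that calculation.** 0.608 + 1.2816·√(0.608·0.392/17) = 0.760. Multiplied by 17 this is 12.9, so at least 13 of 17.

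**3. Do common methods agree?** Complete 3-year status is assumed, and s is the proportion disease free. Success means score z > 1.2816, a one-sided 90% lower bound above 60.8%, or exact p ≤ 0.10.

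- Score: z = (s − 0.608)/√(0.608·0.392/n)
- Wald bound: s − 1.2816·√(s(1−s)/n)
- Complementary log-log bound: s^exp(1.2816·se), with se = √((1−s)/(n·s))/|ln s|
- Exact: P(X ≥ x) for a binomial with p = 0.608

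| Result | Score z | Wald bound | Compl. log-log bound | Exact p | Outcome |
|---|---|---|---|---|---|
| 12/17 | 0.83 | 56.4% | 53.8% | 0.287 | all fail |
| 13/17 | 1.32 | 63.3% | 60.0% | 0.140 | split 2–2 |
| 14/17 | 1.82 | 70.5% | 66.5% | 0.053 | all succeed |
| 13/18 | 0.99 | 58.7% | 56.1% | 0.229 | all fail |
| 14/18 | 1.475 | 65.2% | 62.0% | 0.106 | only exact fails |
| 15/18 | 1.96 | 72.1% | 68.2% | 0.038 | all succeed |

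Exactly 13 of 17 has probability 16.5% if 3-year DFS is 83.8%, and 8.7% if it is 60.8%.

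**4. Exact properties of each cut-off.**

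| Rule | Alpha at 60.8% | Power at 83.8% |
|---|---|---|
| ≥13/17 | 0.140 | 87.3% |
| ≥14/17 | 0.053 | 70.8% |
| ≥14/18 | 0.106 | 84.6% |
| ≥15/18 | 0.038 | 66.8% |

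No cut-off at 17 or 18 has both exact alpha ≤0.10 and power ≥80%. The smallest n that does is 19 (≥15/19: 0.079, 81.7%).

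**5. Can the median be reached?** Assume constant hazard and no early censoring. The plan's own null fits constant hazard: 0.19^(3/10) = 0.608. The median is 3·ln 2/(−ln S3), where S3 is 3-year DFS: 11.8 years at 83.8% and 4.2 years at 60.8%. Observation is 5.0 years, or 5.4 years from day 1 (21 weeks plus 5 years). The median is reached when at least 9 of 17 or 18 patients have an event.

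| True 3-year DFS | n=17, 5.0 / 5.4 years | n=18, 5.0 / 5.4 years |
|---|---|---|
| 83.8% | 1.4% / 2.2% | 2.2% / 3.3% |
| 60.8% | 70% / 78% | 78% / 85% |

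**The case against.** Much of the plan is in place. Section 3.1.1 gives the endpoint, time origin, events and estimator. Section 9.2 fixes the null, the side and, in its text, alpha. DFS is not a secondary objective in 2.2 except in its correlation with PD-L1, so the DFS line in 9.3 can only be the primary analysis under the wrong heading. Sections 2.1.1, 3.1.1 and 9.1 speak of estimation, and no section ties a go/no-go decision to the result. A 3-year Kaplan-Meier estimate with an interval would meet the objective as written.

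This stands, and it rules out three stronger readings:

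- *The plan has no method for its primary endpoint.* It has an estimator in 3.1.1. What is missing is the test or interval, and agreement between 9.3 and 3.1.1.
- *The success criterion is left to be chosen after the data are seen.* The inputs in 9.2 imply ≥13/17 in advance, and the methods compared split at only one count for each n.
- *The 14.0% contradicts the stated 10%.* The 10% is the nominal level of a normal approximation, and the 14.0% is that rule's exact level with complete data. Both can be true.

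The objection does not remove the rest. Section 1.1 states a comparison with historical control, and 9.2 claims power and alpha for it. Those are properties of a rule that no section writes down, and 9.3 as worded points to a different quantity.

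**Conclusion.** The point holds as a mismatch between sections. The endpoint definition and the sizing concern 3-year DFS, while the analysis section gives only the median, which does not address the 60.8% null. If 3-year DFS is 83.8%, the median would be reached in only 1.4–3.3% of trials. If it is 60.8%, it would be reached in 70–85%, so the line is uninformative mainly in the case the trial hopes for. Those figures rest on constant hazard and no early censoring.

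The unnamed test or interval matters at one count for each sample size, 13/17 or 14/18, assuming complete 3-year status. The exact operating characteristics also differ from the nominal ones, and no rule at 17 or 18 meets both stated targets exactly. The correction should be made because it concerns the primary endpoint and needs only text.

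**What to change.** 1. Delete the word median from 2.1.1 and 9.1.
2. Add to 9.3: *Primary analysis: Kaplan-Meier estimate of DFS at 36 months from D1 with its one-sided 90% lower confidence bound (complementary log-log), compared with 60.8%, performed when every patient has had an event, completed 36 months of follow-up, or been withdrawn or lost to follow-up. Patients without an event are censored at last disease assessment.* Add that a cohort with no events counts as exceeding 60.8%, because this bound cannot be computed at 100%. Keep median DFS as descriptive.
3. In the 23% column of the 9.2 table, change alpha from 0.010 to 0.10.
4. Reconcile 17 evaluable (9.2) with 18 evaluable (1.1) and name one analysis set.
5. Restate alpha and power in 9.2 as the exact figures of this rule. With complete data the bound succeeds at ≥14/18 (alpha 0.106, power 84.6%) if all 18 are analysed, or at ≥14/17 (0.053, 70.8%) if 17 are. State that neither meets both alpha ≤0.10 and power ≥80%. The n of 19 that would do so is given for disclosure only, not as a request to enrol more.

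Cost: wording in 1.1, 2.1.1, 9.1, 9.2 and 9.3, with no new patients, data or follow-up. The downside is that 80% power at alpha 0.10 gives way to less tidy figures.

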2.2 Secondary Objectives

- 2.2.1 To characterize safety by evaluating Grade 3-4 acute toxicities of adjuvant durvalumab with radiotherapy in intermediate-risk HNSCC patients
- 2.2.2 To characterize the Grade 3-4 chronic toxicities of adjuvant durvalumab with radiotherapy in intermediate-risk HNSCC patients.
- 2.2.3 To characterize any-grade chronic toxicities of adjuvant durvalumab with radiotherapy in intermediate-risk HNSCC patients.
- 2.2.4 To estimate median OS in patients with intermediate-risk HNSCC treated with adjuvant durvalumab with radiotherapy.
- 2.2.5 To correlate PD-L1 expression with disease free survival

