3.2 Secondary Endpoints

- 3.2.1 Grade 3-5 acute toxicity will be evaluated according to guidelines from NCI CTCAE, v5.0 and include toxicity from the first day of treatment with immunotherapy until 30 days after completion of concurrent immunotherapy and radiation. Toxicity will include all toxicity attributed to the total study regimen (inclusive of radiation) not just to durvalumab alone.
- 3.2.2 Grade chronic 3-5 toxicity will be evaluated according to guidelines from NCI CTCAE, v5.0 and include toxicity continuing or occurring 30 days after completion of concurrent immunotherapy and radiation, and will be followed for up to 6 months.
- 3.2.3 OS will be estimated via the Kaplan-Meier method. OS is defined as the time from D1 of treatment to death from any cause.

3.2.4 Measure PD-LI expression by immunohistochemistry. Pre-treatment PD-L1 expression will be correlated with disease free survival following treatment of adjuvant durvalumab with radiotherapy

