7.0 EVALUATIONS AND ASSESSMENTS

7.1 Time and Events Table

Assessments	Screening ^{2, 3}	Study Treatment ³						End of Treatment ⁴	3&6 months after completion of study therapy ³	At Time Disease Recurs ³	Long Term Follow-up ^{3,4,14}
		C1 D1	C2 D1	C3 D1	C4 D1	C5 D1	C6 D1				
Informed Consent	X										
Dental Exam ¹	X										
Physical Exam and Medical History ²	X	X	X	X	X	X	X	X	X		X
ECOG Performance status	X	X	X	X	X	X	X	X	X		X
Pregnancy Test ¹⁵	X	X	X	X	X	X	X				
CBC with Differential	X	X	X	X	X	X	X	X	X		
Serum Chemistries and LFTs ¹²	X	X	X	X	X	X	X	X	X		
Amylase and Lipase	X								X		
Thyroid Studies ⁷	X ⁷		X ⁷	X ⁷	X ⁷	X ⁷	X ⁷	X ⁷	X ⁷		
Uric Acid	X		X								
Creatinine Clearance ¹³	X	X	X	X	X	X	X	X			
Concomitant Medicine Review	X	X	X	X	X	X	X	X	X		X
Durvalumab 1500mg IV Q3W		X	X	X							
Durvalumab 1500mg IV Q4W					X	X	X				
Radiation Therapy (Daily, Mon-Friday)		X ¹⁰	X ¹⁰	X ¹⁰							
Tumor Assessment ⁵	X								X		X
Pneumonitis (ILD) Assessment ^{6, 8}			X	X	X	X	X	X	X		X
Clinical Toxicity Assessment ⁶	X	X	X	X	X	X	X	X	X		X
FACT-H&Nv4 (QOL Assessment)		X	X	X	X			X	X		
Standard of care imaging (PET/CT/MRI)					X						
Blood draw to study immune system ⁹		X			X			X	X	X	X
Request for Archival Tissue ¹¹	X										
Surgical biopsy at recurrence										X	
Progression and Survival							X	X			X

Footnotes to Time and Events Table

1. As required per institutional standard of care. Should be obtained 3 weeks before Day 1 if it is required per institutional standard of care.
2. History and physical exam may be performed within 6 weeks prior to day 1 of study treatment. Complete medical history and physical examination (including height, weight, and vital signs) for pre-study assessment; focused medical history and physical examination (including weight) at subsequent assessments. Other evaluations except for pregnancy test and baseline imaging must be performed within 6 weeks prior to Day 1 of study treatment. Serum β -HCG must be performed within 7 days prior to first dose of study medication for women of child-bearing potential. Initial baseline imaging must be within 4 weeks of Cycle 1 day 1.
3. A window of +/- 3 and +7 days applies to all study visits unless otherwise specified. The visits occurring 3 months and 6 months after completion of study therapy have a window of +/-15 days. Long-term follow-up visits will occur per standard of care (SOC). Also note, cycles 1-3 are 3 week cycles and cycles 4-6 are 4 week cycles.

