8.3 Documentation of non-serious AEs or SARs

For non-serious AEs or SARs, documentation must begin from time of signature of informed consent, throughout the treatment period and including the follow-up period (90 days after the last dose of durvalumab).

During the course of the study all AEs and SAEs should be proactively followed up for each patient. Every effort should be made to obtain a resolution for all events, even if the events continue after discontinuation/study completion.

If a patient discontinues from treatment for reasons other than disease progression, and therefore continues to have tumor assessments, drug or procedure-related SAEs must be captured until the patient is considered to have confirmed PD and will have no further tumor assessments.

The investigator is responsible for following all SAEs until resolution, until the patient returns to baseline status, or until the condition has stabilized with the expectation that it will remain chronic, even if this extends beyond study participation.

Collected information should be recorded in the Case Report Forms (CRF) for that patient. Please include a description of the event, its severity or toxicity grade, onset and resolved dates (if applicable), and the relationship to the study drug. Documentation should occur at least monthly.

Adverse events will be recorded using a recognized medical term or diagnosis that accurately reflects the event (CTCAE 5.0 Meddra terms). AEs will be assessed by the investigator for severity, relationship to the investigational product, possible etiologies, and whether the event meets criteria of an SAE and therefore requires immediate notification to AstraZeneca/MedImmune Patient Safety.

The following variables will be collected for each AE:

- AE (verbatim)
- The date when the AE started and stopped
- The maximum CTCAE grade reported
- Changes in CTCAE grade
- Whether the AE is serious or not
- Investigator causality rating against the IPs (yes or no)
- Action taken with regard to IPs
- Administration of treatment for the AE
- Outcome

In addition, the following variables will be collected for SAEs:

- Date the AE met criteria for SAE
- Date the Investigator became aware of the SAE
- Seriousness criteria fulfilled

- Date of hospitalization
- Date of discharge
- Probable cause of death
- Date of death
- Whether an autopsy was performed
- Causality assessment in relation to study procedure(s)
- Causality assessment in relation to other medication

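### Any-grade chronic toxicity is a secondary objective with no endpoint or analysis, and the 6-month chronic window has no anchor and, on the nominal schedule, outlasts routine AE documentation

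*Combined protocol and SAP*

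**What the plan says.** The protocol lists two separate chronic-toxicity objectives. Section 2.2.2 is "To characterize the Grade 3-4 chronic toxicities of adjuvant durvalumab with radiotherapy in intermediate-risk HNSCC patients". Section 2.2.3 is "To characterize any-grade chronic toxicities of adjuvant durvalumab with radiotherapy in intermediate-risk HNSCC patients".

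There is one chronic endpoint, 3.2.2: "Grade chronic 3-5 toxicity will be evaluated according to guidelines from NCI CTCAE, v5.0". It covers "toxicity continuing or occurring 30 days after completion of concurrent immunotherapy and radiation, and will be followed for up to 6 months". The text does not say where the 6 months start.

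There is one chronic analysis, item 1 under the additional secondary objectives in 9.3: "Grade 3-5 chronic toxicities will be tabulated by type and grade".

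On collection, the Time and Events Table (7.1) marks the row "Clinical Toxicity Assessment" at screening, every cycle, end of treatment, the 3- and 6-month visits and long-term follow-up. Footnote 3 counts the 3- and 6-month visits from completion of study therapy, with a window of 15 days either way, and leaves long-term visits to standard of care. Footnote 6 asks for changes in AE severity to be entered in the eCRF throughout the trial. Section 8.3 sets the documentation period for non-serious events from consent through treatment, "including the follow-up period (90 days after the last dose of durvalumab".

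**The concern.** Because 2.2.3 stands beside 2.2.2, the protocol evidently wanted more than severe late events. What 2.2.3 adds is the lower grades, and those are what the endpoint and table leave out. Section 1.2.1 justifies the trial partly by the long-term ear, kidney and nerve damage seen with cisplatin, so lower-grade late effects bear on the rationale.

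The window raises a second problem. Without an anchor, two analysts could draw different chronic-toxicity tables from the same data. If routine documentation of non-serious events stops before the window closes, late new-onset events may be entered at one site and not at another, and the table would then under-count in a way nobody could measure.

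**Working it through.** The documents give no target rate, power or confidence limit for chronic toxicity, so there is no planned figure to reproduce. The check is a comparison of sections followed by a calendar.

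**Step 1. Objective, endpoint and analysis side by side**

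| Quantity | Objective | Endpoint | Analysis in 9.3 |
|---|---|---|---|
| Severe acute | 2.2.1, Grade 3-4 | 3.2.1, Grade 3-5 | Rate with confidence interval |
| Severe chronic | 2.2.2, Grade 3-4 | 3.2.2, Grade 3-5 | Item 1, Grade 3-5 |
| Any-grade chronic | 2.2.3 | None | None |

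Objective 2.2.2 is covered, since a table by grade contains Grades 3 and 4. Objective 2.2.3 has two empty cells. Section 9.3 does also promise rates for individual types and grades of toxicity, but that sentence sits in the acute-toxicity paragraph, while chronic toxicity has its own item limited to Grade 3-5.

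**Step 2. Calendar in weeks from C1D1**

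Inputs: three 3-week cycles then three 4-week cycles (5.2.1); radiation over 6 weeks within the 9 weeks of Cycles 1-3 (5.2); 90 days = 90/7 = 12.9 weeks; 6 months = 26.1 weeks. Assumptions: six doses, no delay, radiation starting at C1D1.

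- Last dose (C6D1): 3 + 3 + 3 + 4 + 4 = week 17. End of Cycle 6: 17 + 4 = week 21.
- End of 8.3 documentation for non-serious events: 17 + 12.9 = week 29.9.
- End of concurrent phase: week 6 (radiation complete) or week 9 (end of Cycle 3).
- Opening of the chronic window, 30 days (4.3 weeks) later: week 10.3 or 13.3.

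| Anchor for the 6 months | Window closes (week) | Weeks after 29.9 |
|---|---|---|
| End of concurrent phase | 6 + 26.1 = 32.1, or 9 + 26.1 = 35.1 | 2.2 to 5.2 |
| Opening of chronic window | 10.3 + 26.1 = 36.4, or 13.3 + 26.1 = 39.4 | 6.5 to 9.5 |
| Completion of therapy (last dose or end of Cycle 6) | 17 + 26.1 = 43.1, or 21 + 26.1 = 47.1 | 13.2 to 17.2 |

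The scheduled 6-month visit falls at week 43.1 counted from the last dose (40.9 to 45.2 with the 15-day window) or week 47.1 from the end of Cycle 6 (44.9 to 49.2). It is therefore outside the endpoint window on both concurrent-phase anchors, and after the end of 8.3 documentation in every case.

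**Step 3. Sensitivity to the ideal schedule**

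Section 12.1.1 allows dose holds. A 3-week hold after radiation moves the last dose to week 20 and the end of documentation to 20 + 12.9 = week 32.9, past the shortest closing time of 32.1. Early discontinuation works the other way: with the last dose at C3D1 (week 6), documentation ends at 6 + 12.9 = week 18.9. If the 6 months run from the last dose, the difference is 26.1 - 12.9 = 13.2 weeks whatever the delays.

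**The case against.** The strongest reply is that the information is not lost. Section 8.3 collects the maximum grade and grade changes for each AE with no Grade 3 threshold, so an any-grade table can be produced at any time. Section 8.3 also asks that all AEs be followed up proactively, even past study completion. Footnote 4 follows Grade 2 or worse and serious events that are ongoing at end of treatment until they resolve or are deemed irreversible. Section 7.5 ties toxicity assessment to the schedule, which includes the 6-month visit. Because 3.2.2 counts continuing as well as new toxicity, much chronic toxicity will have started earlier and is carried by these rules. Finally, the stated toxicity hypothesis (1.1) concerns acute events, and chronic toxicity is descriptive in 18 single-arm patients.

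Most of this stands, and it rules out three stronger readings.

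- A reader might infer that the plan cannot meet its chronic-toxicity objectives. The documents do not support that: 2.2.2 is covered, and 2.2.3 lacks an endpoint and a table, not data.
- A reader might infer that scheduled toxicity assessment stops at 6 months, or that documentation of late events is not required at all. Section 7.1 marks assessment in long-term follow-up, and footnotes 4 and 6 with the follow-up text in 8.3 still apply. What remains is conflicting instructions, chiefly for new-onset, non-serious events after day 90.
- A reader might infer that the endpoint should span the 5-year follow-up in 5.9. No objective sets a horizon beyond 6 months, long-term visits follow standard of care, and footnote 14 names the blood draw as the only study-required evaluation there (possibly meaning laboratory work only). A longer table is a preference.

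The reply does not fill the empty cells for 2.2.3, supply an anchor, or reconcile 8.3 with 7.1.

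**Conclusion.** The point holds in this limited form. One named secondary objective, 2.2.3, has neither endpoint nor analysis, and following the plan leaves it unreported. This part depends on no assumption about timing.

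The window problem is also real but conditional. With six undelayed doses, 8.3 documentation ends at about week 30 and the 3.2.2 window closes at about week 32 to 47, a difference of about 2 to 17 weeks that depends mostly on the unstated anchor. The lower end can vanish with a single dose hold, so the range describes the nominal schedule and is not a guaranteed gap. The likely effect is under-recording of late-onset, non-serious events. No test or decision rule depends on it, and sample size, alpha and power are unaffected. The correction should be made because it is cheap and the objective is the protocol's own.

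**What to change.** 1. Change 3.2.2 and 9.3 item 1 to tabulate worst-grade chronic toxicity by type for all grades, with Grade 3-5 as a subset. This answers 2.2.2 and 2.2.3 in one table.
2. State one anchor for the 6 months. Completion of study therapy is one option, since it brings in the scheduled 6-month visit. Say whether completion means the last dose or the end of the last cycle, and let the window include the 15-day visit allowance.
3. Align the 8.3 documentation period for non-serious events with the end of that window, and reconcile it with footnote 6. Clarify whether footnote 14 covers laboratory tests only or toxicity assessment too.
4. Toxicity from long-term standard-of-care visits may be reported separately as descriptive data; this is optional.

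The cost is one more table and some AE entry at a visit where toxicity assessment is already marked.
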